#### 8.6.3 Other covariates

#### Time of the intervention:

Restrictions for NOMAC were first introduced in 2018, with a transition period from October 2018 to January 2019. Additional EU-level restrictions were implemented in 2020 for products with NOMAC in combination with oestradiol, which were not considered for the study (see limitations for further details).

Regarding the restrictions implemented in 2022, a transition period of three months (November 2022 to January 2023) will be considered to reflect the period during which the intervention was being implemented. This transition period will be applied for all pre- and post-intervention comparisons. For objectives 1 to 5, treatments initiated during this period will be considered for the overall results but not for the stratification by time period (see "Covariates for stratification" below for more information). For objective 6, aggregate monthly figures of this time period will be excluded.

Relevant dates related to the implementation of restrictions in 2018 and 2022 are detailed in Appendix II.

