#### Objective 6:

The impact of the restrictions of use will be estimated using an ITS. This analysis will be restricted to NOMAC and CMA (assessed separately) and will be informed by results of the main analysis obtained as part of objective 1 (no meningioma restriction). For NOMAC, the intervention taken place in 2018 will also be assessed.

Time series will be assessed using segmented regression. Monthly incident counts of patients prescribed with NOMAC or CMA will be modelled using a Poisson regression model. Quasi-Poisson models will be considered in the presence of overdispersion. The effect size of the intervention will be estimated using risk ratios (RR).

The assumption of linearity will be assessed by visually inspecting the data and residuals, as well as through statistical goodness-of-fit tests. Autocorrelation will be assessed by examining the plot of residuals and the partial autocorrelation function and conducting statistical tests where possible. If seasonality is detected, it will be controlled for by including variables representing them in the regression model. If the trends are not (or cannot be transformed to be linear) or in the presence of residual autocorrelation, ITS will not be conducted due to the complexity of predicting the counterfactual and to disentangle the intervention effects.(23)

Authors: [name], [name], [name], [name], [name]

Version: V4.0

Dissemination level: Public

The impact model of the intervention (i.e. how we expect the intervention has impacted the outcome) is anticipated to show an abrupt change in the level and a gradual change in the gradient of the trend (step and slope change). Potential impact models will be further discussed and agreed with EMA and defined a priori.(23, 24)

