The amount of pre-intervention data to include for this analysis will be based on defining a valid counterfactual for the ITS analysis. Given the large amount data (12 years before the intervention), the range of pre-intervention data will be restricted to ensure the validity of the comparison (i.e. historical trends might differ from the most recent ones). To analyse the impact of restrictions adopted in 2022, analysis will be conducted using data from 1st January 2021 onwards. For NOMAC, the intervention adopted in 2018 will be assessed using data from 1st January 2017 onwards. Methodological considerations will be evaluated based on the visual assessment of the trends. This may include adjustments on the amount of pre-intervention data or the frequency of data points, if deemed necessary to support the analysis.

Results will be reported overall and stratified by dose (high- vs. low- dose products) and indication (non-HRT vs. HRT).

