#### A. Primary analysis

Hypothesis:	Objective 1: Not applicable, descriptive analysis.
	Objective 2: Cumulative dose and duration of treatments with NOMAC or CMA will be lower after the implementation of restrictions.
	Objective 3: The number of new users of NOMAC or CMA with prior history of meningioma will be reduced after the implementation of restrictions.
	Objective 4: The number of users initiating NOMAC or CMA as first-line treatment will be reduced after the implementation of restrictions.
	Objective 5: The number of discontinuations and switches from NOMAC or CMA to other drug classes will increase after the implementation of restrictions.
	Objective 6: The incidence of NOMAC or CMA will be reduced after the implementation of restrictions, especially for high-dose products. This reduction will not be observed for other drug classes of interest.
Exposure contrast:	Objective 1: Not applicable, descriptive analysis.
	Objective 2: Pre-intervention (1-year period) vs. Post-intervention (1-year period)
	Objective 3 to 6: Pre-intervention vs. Post-intervention
Outcome:	Objective 1: Incidence rates and prevalence of drug classes of interest
	Objective 2: Cumulative dose and treatment duration of NOMAC or CMA.

Authors: [name], [name], [name], [name], [name]

Version: V4.0

Dissemination level: Public

	Objective 3: Number and characteristics of users of drug classes of interest.
	Objective 4: Line of treatment when initiating NOMAC or CMA.
	Objective 5: Diagnosis with meningioma during treatment. Discontinuations and switches
	from treatments with NOMAC or CMA to others.
	Objective 6: Incidence rates of NOMAC or CMA.
	Drug classes of interest, NOMAC and CMA will be assessed separately.
Analytic software:	R
Model(s):	Objective 1: Not applicable, descriptive analysis.
	Objective 2 to 5: Standardised mean differences.
	Objective 6: Segmented regression (Poisson models).
Confounding adjustment method	
	Stratification.
Missing data methods	
	The absence of a record for a condition or medication will be considered as the absence of the disease or use of the medication.
Subgroup Analyses	
	Objective 1: Age groups, indication, study period. For NOMAC or CMA only: dose, WHO ATC 5 th level (if counts allow). A subgroup analysis will be performed restricting the study population to individuals with a prior history of meningioma.
	Objective 2: Study population, indication, study period.
	Objective 3: Study period.

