#### **Databases:**

In IQVIA LPD Belgium and IQVIA DA Germany, the observation period of the patients in these databases is calculated based on the last visit, observation or interaction of the patient with the health care system. This methodology impacts the individuals considered "at risk" for the different medicines of interest of the study (i.e., the individuals included in the denominator populations) during the latest months of available data from the latest data lock, where healthy and/or non-frequent users of the health care system will not be considered active. Consequently, the denominators that will be used to calculate the incident use of drugs in the population may present an artefactual decrease whilst the incident users will remain, incrementing the incidence and prevalence ratios. The presence of these artefacts will be considered when interpreting the results. However, this is likely to affect the amount of follow up available for the study. We expect that the data from the last 6 months may not accurately reflect actual figures of use and, therefore, will be excluded from the analysis for Objective 1 and 6.

Regarding the study period, NAJS will provide data from 2017 onwards only, as prior data might include information on duplicated patients. IQVIA LPD Belgium will provide data from 2012 onwards.

Since information on drug exposure end dates is unavailable in NAJS, treatment duration will not be inferred directly from the start and end dates of drug exposure. Instead, we will infer the treatment period using only the drug exposure start dates, assuming continuous drug exposure between consecutive start dates, if separated by less than 90 days. To account for the final prescription, we apply a 30-day window following the last recorded drug start date. This approach might lead to some uncertainty regarding the exact duration or cumulative dose prescribed.

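### Objective 6 defaults to Poisson errors and leaves the switch to quasi-Poisson conditional, a switch that series of about 24 to 31 months would often fail to trigger under moderate overdispersion

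*Protocol*

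**What the plan says.** Section 8.8, Objective 6, sets the error model: "Monthly incident counts of patients prescribed with NOMAC or CMA will be modelled using a Poisson regression model". The next sentence adds the condition: "Quasi-Poisson models will be considered in the presence of overdispersion". No test, threshold or dispersion value is given. The anticipated impact model is a "step and slope change", and the effect is reported as risk ratios. Table 11, under Model(s), lists "Segmented regression (Poisson models") and does not mention quasi-Poisson.

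Three other statements fix the length of the series for the 2022 measures:
- The data start in January 2021 (Section 8.8, Objective 6).
- For the transition months, November 2022 to January 2023, Section 8.6.3 says that "aggregate monthly figures of this time period will be excluded".
- Section 11, Databases, says of the last six months in the two IQVIA sources that they "will be excluded from the analysis for Objective 1 and 6".

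**The concern.** A Poisson standard error assumes that the variance equals the mean. If monthly counts vary more than that, the standard error is too small by the square root of the dispersion, even when the months are independent. The planned safeguard is a look at the data followed by a possible change of model. In short series such a look has little power against moderate overdispersion, so a series that passes it may still carry intervals that are too narrow. The word chosen for the switch also leaves open whether a positive finding must be acted on.

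The risk ratio from Objective 6 is the only model-based estimate of the effect of the measures: Objective 1 is descriptive and Objectives 2 to 5 use standardised mean differences. It is estimated for two substances in three databases, overall and by two dose and two indication strata. That makes up to 2 x 3 x 5 = 30 series for 2022, before the 2018 NOMAC series.

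**Working it through.** The protocol has no dispersion or precision figure to reproduce, so the check starts from the number of months.

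**Months per series**
- Before: January 2021 to October 2022 = 12 + 10 = 22.
- Germany: lock 30 September 2023, less six months, so the series ends in March 2023. After: February and March = 2. Total 24.
- Belgium: lock 31 December 2023, less six months, so it ends in June 2023. After: 5. Total 27.
- Croatia: lock 17 November 2023, complete months only, so it ends in October 2023. After: 9. Total 31.

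Without the six-month exclusion Germany would have 30 points and Belgium 33. The length of the 2018 NOMAC series is not covered here.

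**Chance of missing overdispersion**

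The step-and-slope model has 4 mean parameters (intercept, trend, step, slope change), so the residual degrees of freedom are n - 4. The assumed check is a one-sided 5% Pearson test. With variance = φ x mean:

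P(miss) = P(χ²_df < χ²_df(0.95) / φ)

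| Series | df | χ²(0.95) | divided by 1.5 | miss, φ = 1.5 | miss, φ = 2 |
|---|---|---|---|---|---|
| Germany, 24 | 20 | 31.41 | 20.94 | 60% | 27% |
| Belgium, 27 | 23 | 35.17 | 23.45 | 57% | 22% |
| Croatia, 31 | 27 | 40.11 | 26.74 | 52% | 17% |

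Simulations put the φ = 2 miss at about 16-28%. At φ = 1.2 the formula gives 82-84%, but little is lost there; at φ = 3 it gives 1-4%. With 2 to 4 seasonal terms the miss at φ = 1.5 becomes 54-65%. If the rule were instead an estimated dispersion above 1.5, the miss would be 54% at φ = 1.5 and 18-22% at φ = 2.

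**Effect on the interval for the step**

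At φ = 1.5 the Poisson standard error should be √1.5 = 1.22 times larger. A nominal 95% interval then reaches only 1.96 / 1.22 = 1.60 true standard errors, which covers about 89%.

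Simulation used 10,000 series per setting, negative-binomial counts with variance φ x mean, independent months, an assumed mean level of 20 or 100 per month, and the three series lengths above. Coverage of the 95% interval for the step was:

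| φ | Poisson kept | test, then choose | quasi-Poisson throughout (t) | same, dispersion floored at 1 |
|---|---|---|---|---|
| 1 | 94.9-95.6% | 95.0-95.8% | 94.7-95.5% | 96.5-97.5% |
| 1.5 | 88.6-89.8% | 92.4-93.4% | 94.8-95.5% | 95.1-96.0% |
| 2 | 83.7-84.7% | 93.6-94.1% | 94.9-95.6% | 94.9-95.8% |

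Among series at φ = 1.5 that passed the test and kept Poisson, coverage was 88.6-90.0%. As error rates (100% minus coverage) at φ = 1.5, these are 6.6-7.6% for test-then-choose, 10.2-11.4% for Poisson kept and 4.5-5.2% for quasi-Poisson throughout. A further simulation of the 5% test of the step at φ = 1.5 gave 6.4-8.0%, 10-12% and 4-5%.

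**The case against.** The protocol already recognises overdispersion and names the right remedy; the disagreement is only about order, and both orders are common practice. That stands, and it limits the weight of the point. How dispersion is judged may also be left to an analysis plan. That stands for the missing test and threshold, which are not criticised here. It does not cover the default model and the conditional switch, because the protocol states both.

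The dispersion of 1.5, the 5% test and the monthly means are not in the documents. This stands in full. The protocol offers reasons why extra variation is plausible: it expects COVID-19 effects possibly lasting into 2021, and the Belgian data come from a panel of 300 GPs. It offers no measurement of it.

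Three stronger readings are tempting and are not supported:
- A reader might infer that the Objective 6 intervals are too narrow in general. They are so only where overdispersion exists and is missed or not acted on; at φ = 1 the planned rule covers 95-96%.
- A reader might take the 10-12% error rate as that of the plan. It applies only if Poisson is kept even where overdispersion was detected, which the text leaves possible but does not plan.
- A reader might see Table 11 as a contradiction. Section 8.8 introduces that table as a summary, so its entry can be read as shorthand for the model class.

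Finally, the protocol reports risk ratios and fixes no significance test of the step. The error rates are therefore best read as the complement of interval coverage.

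**Conclusion.** The point holds as a modest, inexpensive improvement. The protocol fixes a Poisson default with an uncommitted, data-driven switch, and the 2022 series of about 24, 27 and 31 months are too short for that switch to be reliable against moderate overdispersion. Assuming a variance of 1.5 times the mean and a 5% Pearson test, the miss rate is 52-60%, highest in Germany; it falls to about 16-28% at 2 times the mean. If a positive check is always acted on, the cost is an error rate for the step of about 6-8% instead of 5% at 1.5 times the mean, and about 6% at 2 times. If it is not acted on, the rate at 1.5 times the mean is 10-12%. The results assume independent months, no seasonal terms unless stated, and the data locks in Table 3; Section 8.8 also allows the span and frequency of the data points to be changed.

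**What to change.** In Section 8.8, Objective 6, state quasi-Poisson segmented regression as the model for every series from the start: standard errors scaled by the square root of the Pearson dispersion, and 95% intervals from the t distribution on the residual degrees of freedom. Delete the conditional sentence and report the dispersion estimate for each series. Change the Model(s) entry for Objective 6 in Table 11 to match. Flooring the dispersion estimate at 1 is optional; say which is used.

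The cost is one argument in the model call and two small text edits. With 20 to 27 degrees of freedom the t multiplier is 2.09 to 2.05 instead of 1.96, so intervals are about 5-6% wider from that source. When there is no overdispersion the test size is about 5% without the floor and about 3% with it, so the floor makes the analysis slightly conservative.

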#### Analysis:

Due to the limited number of feasibility counts for meningioma (in the order of hundreds across most databases), studying the effect of the restrictions of use among this population will not be feasible. A subgroup analysis for this population has been included for Objective 1 for descriptive purposes; however, it is unlikely to have a sufficient number of patients to allow for formal analysis.

The dates of the interventions were determined based on EU-level restrictions. However, we excluded the restrictions imposed in 2020 on products containing NOMAC in combination with oestradiol (see the introduction for further details). The rationale for this exclusion is that the 2020 intervention is likely to have been affected by the coronavirus disease (COVID-19) pandemic. Including this restriction could result in biased estimates, as any observed effects might be attributed to the pandemic rather than the intervention itself. The effect of the COVID-19 pandemic might still be seen in 2021, which will affect the ability to capture stable trends for Objective 6. Methodological considerations for Objective 6 will be thoroughly evaluated based on the visual assessment of the trends. Regarding the timing of interventions, some countries may have implemented national-level measures prior to the EU restrictions. These measures fall outside the scope of this study and will be considered for context and interpretation only.

The amount of current available data might not fully capture the long-term effects resulting from the RMM implemented in November 2022. Further studies using additional follow-up data (once available) might be needed to assess the long-term impact of the intervention.

Segmented regression (Objective 6) might not be appropriate if trends cannot be transformed to be linear or if there is residual autocorrelation. Other modelling approaches such as Autoregressive Integrated Moving Average (ARIMA) models could be considered. However, these methods require a substantial number of time points before and after the intervention and are not feasible given the currently available post-intervention data.

Authors: [name], [name], [name], [name], [name]

Version: V4.0

Dissemination level: Public

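### Objective 6 sets default series starts but lets window and data frequency be changed after the outcome trends are seen, with no criterion and no duty to report the default result

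*Protocol*

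**What the plan says.** Protocol section 8.8, Objective 6, models monthly incident counts by segmented Poisson regression (quasi-Poisson if overdispersed) and reports risk ratios. The series for the 2022 measures uses data from "January 2021 onwards", and the series for the 2018 nomegestrol measure uses data from "January 2017 onwards". The stated reason is a valid, recent counterfactual. The paragraph then continues: "Methodological considerations will be evaluated based on the visual assessment of the trends". And: "This may include adjustments on the amount of pre-intervention data or the frequency of data points, if deemed necessary to support the analysis".

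Section 11 (Limitations, Analysis) repeats the permission, "Methodological considerations for Objective 6 will be thoroughly evaluated based on the visual assessment of the trends", directly after warning: "The effect of the COVID-19 pandemic might still be seen in 2021, which will affect the ability to capture stable trends for Objective 6".

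Three other provisions bear on this:
- Section 8.6.3, on the transition months November 2022 to January 2023: "For objective 6, aggregate monthly figures of this time period will be excluded".
- Objective 6, on the shape of the effect: "Potential impact models will be further discussed and agreed with EMA and defined a priori".
- Objective 6 also says that no ITS is run if trends cannot be made linear or if residual autocorrelation remains.

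No confidence level, alpha or sidedness is stated for Objective 6. The 95% intervals are stated for Objective 1.

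**The concern.** In a segmented regression the counterfactual is the pre-intervention line carried forward, so the first month of the series helps to determine the estimated effect. The trends to be inspected are the Objective 1 incidence series. The data locks in Table 3 run from September to December 2023 and the code is to be run in March/April 2025, so the plotted series will already show months after the measures. The hypothesis in Table 11 is directional: incidence falls.

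Someone who has seen those points may settle, without intent, on a window or frequency that shows the expected fall. The text does not restrict the inspection to pre-intervention months, list permitted alternatives, give a trigger, or require the default result to be shown beside any replacement. Analyses are run separately by drug and database, with dose and indication strata, so the choice may arise many times. Objective 6 is the study's only model-based estimate of the effect of the measures.

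**Working it through.** **1. Is there a stated figure to reproduce?** No. Objective 6 has no alpha, power or expected count, and section 8.7 says no sample size was calculated. The size of the problem therefore has to be simulated on assumed counts.

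**2. Points under the default (2022 measures).**
- Before: January 2021 to October 2022 = 12 + 10 = 22 months.
- After, Germany: lock 30-09-2023, less the last 6 months (section 11), ends March 2023; February–March = 2.
- After, Belgium: lock 31-12-2023, less 6 months, ends June 2023; February–June = 5.
- After, Croatia: lock 17-11-2023, complete months to October 2023; February–October = 9. The six-month exclusion stands in the paragraph on the two IQVIA databases and is not applied here.
- 2018 measure, before: January 2017 to September 2018 = 12 + 9 = 21 months.

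**3. Model.** log μ(t) = β0 + β1·t + β2·D(t) + β3·D(t)·(t − T), where D = 1 from February 2023 and T is that month. Transition months are dropped. The step risk ratio is exp(β2). The counterfactual exp(β0 + β1·t) depends on the start month through β0 and β1.

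**4. False positives, straight log-linear trend, no effect.** Assumptions: Poisson counts with mean 30 or 150 a month; 5 or 9 post months; starts in January of 2018, 2019, 2020, 2021 and 2022; Wald test at an assumed two-sided 5%.

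| Rule | Any significant step | Significant fall |
|---|---|---|
| Fixed January 2021 | about 4–6% | about 2–3% |
| At least one of five starts | about 10–13% | about 5–7% |

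The second row is an upper bound, reached only if the choice is made for significance. If the five analyses were independent, the figure would be 1 − 0.95^5 = 22.6%. The windows overlap, so the real figure is lower.

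**5. Adding the frequency choice.** Assumptions: starts January 2019, January 2020, January 2021, July 2021 and January 2022; monthly or, where feasible, two-monthly points; 20, 50 or 300 users a month; 2, 5 or 9 post months; with or without a slope change. The fixed default gave 3.3–5.6% two-sided and at least one of 5 to 10 specifications gave 8.7–16.1%. Choosing the specification by lowest dispersion, that is by fit and not by effect, gave 4.8–7.2%. Within one data set, the median ratio of largest to smallest risk ratio was 1.06 to 1.37.

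**6. Shift of the estimate when the trend is not straight (no effect of the measures).**
- Flat until the start of 2021, then falling 15% a year (Belgium and Croatia): median step risk ratio 1.00 from January 2021, 0.93–0.95 from January 2020, 0.88–0.90 from January 2019. At least one specification was significant in 18–98% of runs; choice on fit gave 5.7–9.4%.
- Assumed 20% COVID-19 dip in March–June 2020, recovering by December 2021: step risk ratio 1.07, 1.04, 0.95, 0.95 and 1.00 for January starts 2018 to 2022.

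In the second case the default start itself gives 0.95 when the truth is 1.00.

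**The case against.** **Purpose.** The flexibility is meant to secure a valid counterfactual, and section 8.7 favours recent, balanced data. That points to later starts, while several alternatives above are earlier. This is fair on intent. It is why the inflated rates are upper bounds, with about 5–9% if the choice follows fit alone. Intent does not supply a rule, however.

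**The no-ITS condition protects.** In part. Under the 20% dip at 150 users a month, the 2018 and 2019 starts failed a deviance or Ljung-Box check in 98% of runs. At 30 a month only 27% failed.

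**The default may be the larger problem.** Under the same dip, false falls were 11.7% with January 2021 fixed and 12.3% with the best of five starts passing the checks (150 a month), and 7.3% against 8.8% (30 a month). Choice of window adds little there. This stands: January 2021 must not be treated as unbiased, and other starts need to be shown.

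**Such detail belongs in an analysis plan.** A list of sensitivity starts might. Here, though, the protocol itself grants the override of its own stated windows.

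**Stronger readings that the document does not support.** A reader might infer that a promised error rate is broken, but none is stated for Objective 6. A reader might infer that the override contradicts the commitment to define matters in advance, but that commitment covers the impact model (step or slope), not window or frequency. A reader might also take the 10–13% as the rate of false falls. It counts significant changes in either direction.

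**Conclusion.** The point holds as a risk. The protocol fixes sensible default starts, then permits their replacement after the outcome series has been seen, with no criterion and no obligation to show the default. If the choice follows the apparent effect, the two-sided false-positive rate for the step roughly doubles, from about 5% to at most about 10–13% over five starts, and false falls rise from about 2–3% to 5–7%. Allowing frequency changes as well takes the two-sided upper figure to about 16%. Curvature in the trend can make it far worse.

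All of these rates rest on assumed counts, trends and candidate windows, and on a 5% level that the protocol does not state. Loss of nominal error or coverage is possible, not certain. The dependence of the risk ratio on the start date is the firmer result. Section 11 itself expects instability in 2021, and a reader given a single chosen window could not see how much it matters.

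**What to change.** In section 8.8, Objective 6, replace the last two sentences of the paragraph on the amount of pre-intervention data with:

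> Where the ITS is conducted under the linearity and autocorrelation conditions above, the monthly series from January 2021 (2022 measure) and from January 2017 (2018 measure, where data allow) is the pre-specified analysis and is reported alongside any other. Any change to the amount of pre-intervention data is decided on pre-intervention months only (to October 2022; to September 2018), before post-intervention points are inspected. A change of frequency may be made for sparse or masked counts, without reference to the direction of the effect, and is reported with its reason. Results under alternative start dates (2022 measure: for example January 2020 and January 2022; 2018 measure: earlier starts where the database allows) are reported as sensitivity analyses, and any dependence of the RR on the start date, including residual COVID-19 effects in 2021, is stated in the conclusion.

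Align the matching sentence in section 11. This wording keeps the no-ITS condition, gives the 2018 measure its own series, and leaves room for sparse or masked (<5) counts. Croatia, whose data are used only from 2017, has no earlier start for the 2018 measure.

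The cost is a few extra fits on aggregate counts that Objective 1 already produces, and less freedom to rescue an awkward series.
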